5.4 POTENTIAL BENEFITS

As a Phase 1 sighting Study, the efficacy (benefits) of combining palliative radiation therapy and idronoxil (NOX66) is not known. The hypothesis, however, is that the effect of idronoxil in sensitizing the cancer cells to radiation therapy will provide an enhanced response to this treatment, with a clinical response observed in the patients participating in the trial.

6 STUDY OBJECTIVES AND HYPOTHESES

6.1 PRIMARY OBJECTIVE

- To determine the safety and tolerance of idronoxil, administered as the NOX66 formulation in escalating dose cohorts and concurrently with palliative radiation therapy, in patients with end stage castrate resistant prostate cancer.

6.2 SECONDARY OBJECTIVES

- To investigate whether idronoxil administered as the NOX66 formulation will sensitise end stage prostate cancer to palliative radiation therapy and provide a clinically relevant response to treatment according to:
 - RECISTv1.1 criteria for measurable lesions, within irradiated and non-irradiated target lesions
 - Improvement in total pain scores using BPI-SF instrument
 - To observe changes in serum PSA
 - Review of CT/MRI scans by Radiation Oncology Expert Committee –assessment of observable and or symptomatic changes from baseline over time
- To determine a dose of NOX66 to continue into late phase clinical trials
- To investigate plasma idronoxil levels following NOX66 therapy
- To determine Progression Free Survival (PFS) and Overall Survival (OS)

7 STUDY DESIGN

This is an open-label Phase Ib dose confirmation and proof of concept study in up to 24 patients with end stage castrate resistant prostate cancer who are being considered for or undergoing palliative radiation therapy for pain and symptom management. Patients will have a minimum of one (1) lesion which is amenable to radiation therapy. Palliative RT (20Gy over 5 fractions) will be delivered to selected lesion in combination with rectally administered idronoxil (NOX66).

This study is intended to provide information regarding the safety of this treatment combination and justification for a larger Phase 2/3 study in the treatment of patients with combination of NOX66 and palliative radiation therapy.

Clinical response to treatment will be assessed by radiological CT/MRI scans, where applicable objectively measures by RECISTv1.1, by pain response as evaluated by Brief Pain Inventory Short Form, ECOG scores and by monitoring PSA as surrogate marker with overall (observable and symptomatic) response based on data review by an independent Radiation Oncology Expert Committee (ROEC). Local response will be based on investigator review of data in conjunction with ROEC.

PSA will be monitored as a surrogate marker of response and pain response will be evaluated using the Brief Pain Inventory Short Form throughout the study.

Patients will be suitable for the study as they become eligible for, and will be given, palliative radiation therapy for management of their cancer.

Three dose cohorts will be investigated in this study with dosing based on criteria outlined in section 10.2.7. The three doses of idronoxil investigated include:

- 400mg idronoxil provided as one NOX66 suppository per day
- 800mg idronoxil provided as one NOX66 suppository twice daily
- 1200mg idronoxil provided as one NOX66 suppository three times daily.

Treatment will be for one cycle of combined radiation therapy and NOX66 with follow up assessments at Week 6, Week 12, Week 24 and every 3 months for the following 18 months. All patients will be followed up for disease progression and survival information either by retrospective review of medical records or by a physical visit or by telephone follow up call.

8 STUDY PARTICIPANTS

8.1 STUDY POPULATION

Twenty-four patients with metastatic castrate-resistant prostate cancer and scheduled to receive palliative radiation therapy for management of their disease will be enrolled into the study.

There will be no randomization or stratification in the study.

8.2 INCLUSION CRITERIA

Patients must fulfil all of the following inclusion criteria to be eligible to enrol into the study:

1. Provision of informed consent.
2. ≥ 18 years of age.
3. Histologically confirmed prostate cancer and/or PSA of > 100 ng/mL at original diagnosis
4. Metastatic disease evidenced by either CT/MRI imaging or bone scan.
5. Objective evidence of disease progression as defined by either:
 - i. Radiographic progression of in nodal or visceral metastases and bone disease progression with 2 or more new lesions
 - ii. Rising PSA value ≥ 2 ng/ml in at least 3 measurements, at least 1 week apart, with castrate levels of serum testosterone.
6. Eligible to receive palliative radiation therapy to at least one symptomatic lesion for management of disease.
7. ECOG Performance status 0-2.
8. A minimum life expectancy of 24 weeks.
9. Adequate bone marrow, hepatic and renal function as evidenced by:
 - Absolute neutrophil count (ANC) $> 1.5 \times 10^9$ /L
 - Platelet count $> 100 \times 10^9$ /L
 - Hemoglobin > 9.0 g/dL
 - Serum bilirubin $< 1.5 \times$ ULN
 - AST/ALT (SGOT/SGPT) $< 2.5 \times$ ULN for the reference laboratory or $< 5 \times$ ULN in the presence of liver metastases
 - Serum creatinine $< 1.5 \times$ ULN
10. Ongoing androgen deprivation therapy with luteinizing hormone-releasing hormone (LHRH) agonist or antagonist.
11. At least 4 weeks must have elapsed prior to commencement of NOX66 treatment since prior chemotherapy, investigational drug or biologic therapy and any toxicity associated with these treatments has recovered to \leq NCI-CTCAE (version 4.03) Grade 1.
12. At least 21 days must have elapsed following major surgery and any surgical incision should be completely healed.

8.3 EXCLUSION CRITERIA

Patients who have any of the following exclusion criteria are not eligible to participate in the study:

1. Tumour involvement of the central nervous system
2. Uncontrolled infection or systemic disease

3. Clinically significant cardiac disease not well controlled with medication (e.g. congestive heart failure, symptomatic coronary artery disease, angina, and cardiac arrhythmias) or myocardial infarction within the last 12 months
 - Patients with a QTc > 470 msec on screening ECG
4. Concurrent systemic chemotherapy or biological therapy
5. Any situation where the use of suppository therapy is contra-indicated or impractical (eg. chronic diarrhoea, colostomy, ulcerative colitis).
6. Known human immunodeficiency virus (HIV) or Hepatitis B or C (active, previously treated or both)
7. Any subject whose testosterone is not suppressed i.e. is > 0.5nmols/L.
8. Any other reason which, in the opinion of the investigator, will preclude suitable participation in the study.

8.4 SCREEN FAILURE AND STUDY WITHDRAWAL

Patients should begin protocol treatment within 2 weeks of enrolment at screening. Issues that would cause treatment delays longer than 2 weeks should be discussed with the Sponsor. If a patient does not proceed to receive protocol therapy following enrolment at screening, the patient's study enrolment will be cancelled, and the patient will be considered a screen failure. The Sponsor should be notified of screen failures as soon as possible.

Patients will be informed that they are free to withdraw from the study at any time and for any reason. Withdrawal criteria, other than progressive disease, can be defined as one or more of the following:

- an inter-concurrent illness that prevents further administration of idronoxil (NOX66) or radiation therapy;
- an adverse event to the combination treatment that is intolerable;
- the patient withdraws consent;
- the patient dies;
- general or specific changes in the patient's condition render the patient unacceptable for further treatment in the judgment of the Investigator.

In all cases, the reason for withdrawal must be recorded in the CRF and in the patient's medical records. The patient must be followed to establish whether the reason was an adverse event causally related to idronoxil (NOX66), and, if so, this must be reported in accordance with the requirements for adverse event reporting.

Patients will continue to be followed for the duration of the study, unless consent is withdrawn.

8.5 PATIENT REPLACEMENT

Patients who cannot be evaluated as part of the efficacy analysis may be replaced in the study at the discretion of the Sponsor.

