Patient may be contacted by telephone after enrolment as a reminder to start NOX66 administration day prior to attending clinic for radiation therapy.

10.2.3 Treatment Cycle (Days 1-16) - Visits 2 to 7

Treatment will Commence on Day 1 of the Study Visit Schedule (Table 1) and the procedures for Treatment Visits are listed below in Table 1.

Overall, the patient will attend the clinic on 7 days during the Treatment Cycle.

During the Treatment Cycle, the patient will receive treatment of:

- NOX66 (Dose dependent on treatment cohort) for 13 up to 16 consecutive days (Days 1-16), inclusive of weekends and public holidays.
- Palliative radiation therapy (20Gy Dose) in five fractions over 8 days commencing on Day 2 to Day 9. Radiation therapy **not given** on weekends and public holidays.

Table 1. Schedule of Assessments: TREATMENT CYCLE

Period	Pre-RT		RT									Post RT					EoT ³
	D0 (-7)	D 1	D 2	D 3	D 4	D 5	D 6	D 7	D 8	D 9	D 10	D 11	D 12	D 13	D 14	D 15	D 16+1
VISITS	V1 ¹		V2	V3 - V6 ²													V7
NOX66 (Self-administration)		X	X	X	X	X	X	X	X	X	X	X	X	X	X	X	X ⁴
Radiation therapy			X	X													
Physical exam			X														X
ECG																	X
Vital Signs			X														X
Complete Blood Count																	X
Serum chemistry																	X
Urinalysis																	X
Biomarker ⁵	X																X
BPI-SF ⁶ Questionnaire																	X
Concomitant medications/ Adverse Event ⁷ review			X	X													X
Dispense NOX66	X																
Return NOX66																	X

¹Enrolment-Visit to occur after eligibility confirmation (Screening) and prior to V2, to receive NOX66 and education on self-administration

² Patient attend clinic for 5 days in an 8-day period to receive RT. Patient will not attend clinic on days where RT is not conducted

³ End of Treatment (EoT) visit to occur Day following last dose of NOX66

⁴NOX66 dosing continues to Day 16 if there has been (weekend and public holiday -up to 3 days) interruption in RT in Treatment Cycle.

⁵ Biomarkers include idronoxil

⁶ Brief Pain Inventory-Short Form (1991)

⁷ Adverse Event (AE) assessed by Investigator using the NCI CTCAE v4.03 scoring system

10.2.4 Six-Week Follow up (Day 43 ± 5) - Visit 8

Visit 8 will occur 28 days/4 weeks post completion of NOX66 treatment and consist of the following assessments:

- Physical Examination including vital signs
- Performance Status Assessment (using ECOG performance scale)

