10.2.14 Cohort Allocation and Dose Escalation

[figure not shown]
This study will enrol up to 24 patients across three dose levels of NOX66. Dose cohort assignment will be sequential and dose escalation decisions will be based on patients who experience adverse events directly related to NOX66 treatment and discontinued as described below and outlined in Figure 2.

Dose escalation and decision rules are as follows:

- **Patients 1-4 (Dose Cohort 1)** will be prescribed NOX66 400mg.
- **Patients 5-8 (Dose Cohort 2):** Once fourth patient in Cohort 1 has completed treatment (Visit 7), the dose of NOX66 for next cohort, patients 5-8, will be as determined as follows, based on the number of discontinuations due to NOX66 related adverse events:
 - If no patients discontinue treatment, NOX66 dose will be increased to 800mg
 - If one patient discontinues treatment, NOX66 dose will remain at 400mg
 - If more than one patient discontinues treatment, there will be no further recruitment to the study until scans from WEEK 6 are assessed for disease status
- **Patients 9-12 (Dose Cohort 3):** Once the eighth patient in Cohort 2 has completed treatment (Visit 7), the dose of NOX66 for next cohort, patients 9-12, will be as determined as follows, based on the number of discontinuations due to NOX66 related adverse events:
 - If no patients in Dose Cohort 2 discontinue treatment, NOX66 dose will be increased (from 400mg to 800mg or from 800mg to 1200mg)
 - If one patient in Dose Cohort 2 discontinues treatment, NOX66 dose will remain at the same dose (400mg or 800mg)
 - If more than one patient in Dose Cohort 2 discontinues treatment, dose will be reduced (from 800mg to 400mg) or, if dose has remained at 400mg, there will be no further recruitment to the study until scans at WEEK 6 are assessed for disease status.

Following the review of all accumulated safety data, disease status and treatment efficacy signals from scans assessed per RECIST 1.1 criteria and preliminary pain response at WEEK 6 for all patients, the Study Steering Committee will determine the dose at which to continue treatment for the expansion patient Cohort 4 in the study. A further 12 patients will be recruited at this dose level.

Figure 2: Dose Escalation and Dose Expansion Schema

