12.2 STATISTICAL METHODOLOGY

This section describes the planned statistical analyses in general terms. A complete description of the statistical analysis will be specified in a statistical Analysis Plan (SAP) finalised prior to completion of the study.

General: Data will be summarized by using counts and percents for discrete parameters, and by descriptive statistics (e.g. number of observations, mean, standard deviation, median, minimum and maximum) for continuous parameters. Subject disposition and baseline characteristics will be presented for all treated patients. Data will be analysed as collected. No imputation of values for missing data will be performed. Standard clinical monitoring and data management practices will be used to ensure the integrity of the data.

Populations for analysis: There will be two study populations defined for this study. The safety population will consist of all patients who received at least one dose of NOX66. This population will be used in all safety summaries. The efficacy population will consist of all patients who complete radiation therapy with at least 7 days of NOX66 dosing.

Baseline Comparisons and Patient Disposition: Demographic and baseline disease characteristic data summarisation will be performed in order to descriptively document any safety and efficacy findings. Data to be tabulated will include demographic features such as age and race, as well as medical history. The number and percentage of patients who complete the study or who withdraw for any reason will be presented.

Efficacy Analysis: Results from (i) RECIST 1.1 response assessment for target lesions and non-target lesions, (ii) ECOG Performance Score and (iii) Pain scores. Changes from baseline in levels of serum PSA levels will be listed.

Overall and progression-free survival, PSA and pain scores collected during the extended follow-up period will be summarized in the same manner as for the immediate post-treatment follow-up period.

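### Dose escalation needs no minimum exposure from a cohort's first three patients, and the only replacement rule is optional and based on efficacy, so an unrelated early stop counts as a tolerated course

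*Combined protocol and SAP*

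**What the plan says.** All references are to the combined protocol and SAP.

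- **Trigger (10.2.14).** The Cohort 2 dose is set "Once fourth patient in Cohort 1 has completed treatment (Visit 7"), and the Cohort 3 dose likewise after the eighth patient. The synopsis and 13.2 also refer only to the final patient of a cohort.
- **Count (10.2.14).** The decision is "based on the number of discontinuations due to NOX66 related adverse events". For Cohort 1: "If no patients discontinue treatment, NOX66 dose will be increased to 800mg". One discontinuation holds the dose. At the upper end: "If more than one patient discontinues treatment, there will be no further recruitment to the study" until Week 6 scans are assessed. Cohort 2 has the same structure, with a dose reduction from 800 mg as the upper response.
- **Replacement (8.5).** "Patients who cannot be evaluated as part of the efficacy analysis may be replaced in the study at the discretion of the Sponsor".
- **Efficacy evaluability (12.2).** "The efficacy population will consist of all patients who complete radiation therapy with at least 7 days of NOX66 dosing".
- **Planned course (10.2.3).** "NOX66 (Dose dependent on treatment cohort) for 13 up to 16 consecutive days (Days 1-16), inclusive of weekends and public holidays".
- **Never-treated patients (8.4).** "If a patient does not proceed to receive protocol therapy following enrolment at screening", the enrolment is cancelled and he is a screen failure.
- **Oversight (13.2).** The Study Steering Committee (SSC) reviews safety data and determines escalation. No minimum number of evaluable patients is stated for that decision.

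**The concern.** The rule treats every patient without a NOX66-related discontinuation as evidence that the dose was tolerated. A patient who takes a few doses and leaves because of progression, intercurrent illness or withdrawn consent has shown little about tolerability, yet he enters the count as a zero. Two cases follow, reading 8.5 together with 12.2, which is the natural reading although 8.5 does not say so.

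(a) He stops before 7 NOX66 days or before radiation is complete. He may be replaced, but only if the Sponsor chooses.

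(b) He stops after 7 NOX66 days with radiation complete. He is efficacy-evaluable, so 8.5 does not reach him, although up to about half of his NOX66 course is missing.

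In either case the condition for moving from 400 mg to 800 mg, or from 800 mg to 1200 mg, becomes easier to meet, and the trigger of more than one discontinuation becomes harder to reach. Tolerability is the primary objective, and efficacy evaluability is the wrong test for whether a patient informs it.

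**Working it through.** The plan gives no operating characteristics for the escalation rule, so there is no figure to reproduce. The patient numbers are consistent: 3 × 4 + 12 = 24.

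**Inputs from the plan:** cohorts of four; escalation on zero events; course of 13 to 16 days; efficacy threshold of 7 days.

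**Assumptions (the documents give no rates):** true NOX66-related discontinuation rate per full course, p, from 5% to 40%; chance of an unrelated early stop for each of the first three patients, u, 5% or 10%; independent patients; constant daily risk over a 13-day course.

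**Step 1: chance of zero counted discontinuations.**
- Four fully exposed: (1−p)^4.
- One of the first three stops after 1 of 13 days: (1−p)^(3+1/13).
- One stops after 7 of 13 days, case (b): (1−p)^(3+7/13).
- Ceiling, one patient with no exposure: (1−p)^3.

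| p | Four exposed | One stops after 1 day | One stops after 7 days | Ceiling |
|---|---|---|---|---|
| 5% | 0.815 | 0.854 | 0.834 | 0.857 |
| 10% | 0.656 | 0.723 | 0.689 | 0.729 |
| 20% | 0.410 | 0.503 | 0.454 | 0.512 |
| 30% | 0.240 | 0.334 | 0.283 | 0.343 |
| 40% | 0.130 | 0.208 | 0.164 | 0.216 |

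With 7 of 16 days the exponent is 3+7/16. The values at 10% and 30% are 0.696 and 0.293, so course length matters little.

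**Step 2: chance of more than one discontinuation,** 1 − (1−p)^n − np(1−p)^(n−1). At p = 30%:
- n = 4: 1 − 0.2401 − 0.4116 = 0.348.
- n = 3: 1 − 0.343 − 0.441 = 0.216.

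The n = 3 value gives the leaver no exposure, so it marks the largest loss from one patient.

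**Step 3: how often a cohort is affected,** 1 − (1−u)^3: 0.143 at u = 5% and 0.271 at u = 10%.

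**Step 4: average over all cohorts,** last patient complete and leavers given zero exposure: (1−p)(1−(1−u)p)^3.
- u = 5%: 0.667 at p = 10% (0.667 − 0.656 = 0.011) and 0.256 at p = 30% (0.256 − 0.240 = 0.016).
- u = 10%: 0.678 at p = 10% (0.678 − 0.656 = 0.022) and 0.272 at p = 30% (0.272 − 0.240 = 0.032).

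The average shift is thus about 1 to 3 points. It is overstated to the extent that leavers had some exposure or were replaced under 8.5.

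**The case against.** The strongest reply is that escalation is supervised and the effect is small. The SSC decides on safety data and hears at once of related events of Grade 2 or above. Reasons for withdrawal are recorded and followed for causality (8.4). A committee looking at four patients can see that one took a single day of drug. In case (a) the Sponsor can already replace him. The larger assumed rates also sit uneasily with 5.3, which reports no adverse events of Grade 2 or higher with intravenous and oral idronoxil. Unrelated stops must fall within 13 to 16 days, in patients with ECOG 0-2 and a life expectancy of at least 24 weeks.

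Most of this stands, and it limits the weight of the point. It does not remove it. The SSC has no stated minimum to apply, and 10.2.14 makes the increase the stated consequence of a zero count. Section 5.3 also says that the NOX66 adverse event profile is not fully established, so higher rates cannot be excluded.

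A reader might infer that the plan lets the dose rise on three patients with a fourth who contributed nothing. The documents do not support that: a never-treated patient is a screen failure under 8.4, so anyone counted has started protocol therapy, and 0/3 is a ceiling. Nor do they show that any cohort was affected or that any escalation was unsafe. Figure 2, which also outlines the rules, is not available to check.

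**Conclusion.** The point holds as a gap in the stated rule. In the readable text, an unrelated early stop by a treated patient counts as a zero; he need not be replaced, and in case (b) 8.5 does not allow it. With one affected patient, the chance of meeting the escalation condition rises by at most about 7 points at an assumed related rate of 10% (66% to 72%, unrounded 0.656 to 0.723) and about 9 at 30% (24% to 33%). In case (b) it rises by about 3 and 4 points. These sizes rest on assumed rates, constant daily risk and independence. The reason to act is the individual affected cohort: with four patients per decision, one early leaver can remove up to a quarter of the evidence. The plan should be changed, but this is a modest weakness under SSC review and not an uncontrolled risk.

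**What to change.** For Cohorts 1-3, put one definition in 8.5 and 10.2.14. A patient is escalation-evaluable if he:

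1. received a pre-stated minimum share of the scheduled NOX66 doses (for example at least 75-80%, with holds and reductions under 9.4.1 allowed) and was followed to Visit 7; or
2. stopped NOX66 or radiation early for any adverse event related to NOX66 or to the combination, or had a toxicity-driven dose reduction before leaving.

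Patients in group 2 stay in the cohort, are not replaced, and are reviewed by the SSC. This keeps informative tolerability failures in view, including those put down to the radiation part of the combination. The existing count of NOX66-related discontinuations and its thresholds do not change.

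Only a patient who stops short of condition 1 for a reason unrelated to treatment is replaced, at the same dose and before the SSC decides on that cohort. State that replacements are additional to the numbering 1-4, 5-8 and 9-12 and to the total of 24.

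With one patient at a 75% floor, the chance of zero events is (1−p)^3.75: 0.67 at p = 10% and 0.26 at p = 30%, close to the 0.66 and 0.24 for four full courses. A full-course requirement would force a replacement for a stop one day early and gain little.

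The cost is an amendment approved by the Sponsor and SSC, with ethics committee approval or notification (15.4), an occasional delay of a few weeks for recruitment, screening and one course, and possibly a total slightly above 24. Section 10.2.7 refers to patients already past Visit 10, so escalation may have been complete when this version took effect. In that case, report in the SAP and the study report how many patients per cohort met the definition.
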